4.2 PRIMARY ENDPOINT ANALYSIS

There are two co-primary analyses:

- In all randomized patients
- In the MRI-active subgroup

Hypothesis test for the co-primary estimand 1 and for the co-primary estimand 2 is described in Section [2.1](#).

Five attributes of the co-primary estimand 1 and co-primary estimand 2 are provided in [Table 1](#). Further details on the definition of the primary endpoint are provided in [Section 4.2.1](#). Information on primary estimator for co-primary estimand 1 and co-primary estimand 2, intercurrent events and their handling as well as the handling of missing data is described in [Section 4.2.2](#) and [Section 4.2.5](#). [Section 4.2.3](#), [Section 4.2.4](#) and [Section 4.2.6](#), [Section 4.2.7](#) describe sensitivity and supplementary analysis for the co-primary estimand 1 and co-primary estimand 2.

4.2.1 Definition of Primary Endpoint

The primary efficacy endpoint is time to onset of composite 12-week CDP defined as the time from randomization to the first occurrence of at least one of the following progression events:

- **C1:** 12-week CDP in 9-HPT, defined as a 20% worsening from baseline in 9-HPT confirmed for at least 12 weeks
- **C2:** 12-week CDP in EDSS score, defined as an increase of ≥ 1.0 point from baseline EDSS score in patients with a baseline EDSS score ≤ 5.5 or an increase of ≥ 0.5 point in patients with a baseline EDSS score of >5.5 that is confirmed for at least 12 weeks

Initial disability progression can occur at any visit, including unscheduled visits. Four conditions must be fulfilled to satisfy the 12-weeks confirmation criteria for disability progression based on C1 and C2:

1. The confirmation (of disability progression) visit must be at least 12 weeks (84 days) after the initial disability progression.
2. The confirmation visit must be either a scheduled or treatment discontinuation visit.
3. Assessments within 30 days after the onset of a protocol-defined relapse cannot be used for confirmation of the progression.
4. All EDSS or 9-HPT assessments between the initial disability progression and the confirmation visit should also fulfill the requirements of disability progression, i.e., ≥ 1.0 point increase in baseline EDSS if baseline EDSS ≤ 5.5 or ≥ 0.5 increase if baseline EDSS >5.5 , or $\geq 20\%$ increase in 9-HPT from baseline.

If any of the four criteria listed above are not satisfied, then the initial disability progression is not the onset of composite 12-week CDP.

In criteria 3, a protocol-defined relapse is defined as the occurrence of new or worsening neurological symptoms attributable to MS and immediately preceded by a relatively stable or improving neurological state of at least 30 days. Symptoms must persist for at least 24 hours and should not be attributable to confounding clinical factors (e.g., fever, infection, injury, adverse reactions to concomitant medications). The new or worsening neurological symptoms must be accompanied by objective neurological worsening consistent with an increase of at least one of the following:

- Half a step (0.5 point) on the EDSS
- Two points on one of the selected FSS as listed below
- One point on two or more of the selected FSS as listed below

The change must affect the following selected FSS: pyramidal, ambulation, cerebellar, brainstem, sensory, or visual. Episodic spasms, sexual dysfunction, fatigue, mood change, or bladder or bowel urgency or incontinence will not suffice to establish a relapse. Information related to a protocol-defined relapse will be captured on a clinical relapse event case report form (CRF) page.

If the test results for 9-HPT are not available due to a “physical limitation,” the maximum possible value for the scale (16 minutes and 59 seconds) will be imputed. If one of the two trials for the dominant and non-dominant hand is not available and not missing due to a “physical limitation”, the result from the other trial will be used to impute the missing value. Very low values will be considered to be outliers. For outliers, the following rules will be applied. Values outside the lower bound will be treated as missing, and the imputation rule will be applied as defined above. For 9-HPT, the lower bound is 10 seconds ([Oxford Grice et al. 2003](#)).

Composite 12-week CDP in the Presence of Differential Right Censoring

A complicating factor for defining the onset time of the composite 12-week CDP is the presence of differential right censoring in the individual components, i.e., time to 12-week CDP in 9-HPT and time to 12-week CDP in EDSS. In such circumstances, the following algorithm will be used to define the onset time of the composite 12-week CDP:

1. If the onset times of the individual components are all observed, then the onset time of the composite 12-week CDP is the earliest of the observed onset times of the individual components.
2. Otherwise if all onset times of the individual components are right censored, then the onset time of the composite 12-week CDP is right censored at the earliest of the right censored onset times of the individual components.
3. Otherwise if the earliest of the observed onset times occurs prior to or on the same day as the earliest of the right censored onset times of the individual components, then the onset time of the composite 12-week CDP is the earliest of the observed onset times of the individual components.
4. Otherwise if the earliest of the observed onset times occurs after the earliest of the right censored onset times of the individual components, then the onset time of the composite 12-week CDP is set to the earliest of the observed onset times of the individual components.

In scenario 4, the approach to specify the onset time of the composite 12-week CDP as the earliest of the observed onset times of the individual components can in some cases overestimate the true onset time. Nonetheless, the proposed approach is pragmatic and reasonable because it leads to an estimate of the proportion of the composite 12-week

CDP events by the end of the study that is at least as large as the observed proportion, and it has a negligible impact on treatment effect estimation if the independent censoring assumption is plausible for the individual components.

4.2.2 Main Analytical Approach for Co-Primary Estimand 1

The co-primary estimand 1 is the difference in time to onset of composite 12-week CDP, as expressed by the HR, between the experimental and control arms in the MRI-active subgroup of patients with PPMS, including patients later in their disease course, regardless of adherence to the randomized treatment had the patients not initiated another MS disease-modifying therapy (DMT) or commercial ocrelizumab. More specifically, the estimand has the following attributes:

Population: Patients with PPMS, including patients later in their disease course, as defined by the study inclusion and exclusion criteria (see Sections 4.1.1 and 4.1.2 of the protocol), with MRI activity (see Section 2.1.1 of the protocol).

Endpoint: Time to onset of composite 12-week CDP.

Treatment:

- Experimental arm: Ocrelizumab IV 300 mg administered at Day 1 and Day 15, followed by Ocrelizumab IV 600 mg administered every 24 weeks
- Control arm: Matching placebo

Population-level summary: HR for time to onset of composite 12-week CDP

The HR will be calculated from a Cox-regression to estimate the treatment-benefit, and the log-rank p-value will be used to test the statistical significance. Both will be stratified by the stratification factors from the randomization.

In order to estimate the co-primary estimand 1, the following intercurrent event handling strategies will be applied:

Withdrawal from treatment and no initiation of another MS DMT or commercial ocrelizumab: All data pre and post treatment discontinuation will be included in the analysis following the treatment-policy strategy.

Withdrawal from treatment and initiation of another MS DMT or commercial ocrelizumab: Future disease progression in the hypothetical scenario as if no other therapy had been initiated is predicted on the basis of previously observed data and the preceding reason for withdrawal from study treatment.

The following strategies will be used:

- If the patient withdraws from study treatment due to lack of efficacy, a disability progression event will be imputed at the time of initiation of another treatment.

Ocrelizumab—F. Hoffmann-La Roche Ltd

Statistical Analysis Plan WA40404

- Withdrawal from study treatment due to another reason will be:
 - Imputed as a disability progression event if the patient had an initial disability progression at the date of his or her last EDSS or 9-HPT assessment prior to the initiation of another treatment, whichever is the earliest
 - Censored in all other cases at the date of the last EDSS or 9-HPT assessment prior to the initiation of another treatment, whichever is the earliest

For each component (EDSS and 9-HPT), missing assessments at scheduled visits prior to the last assessment of a patient, i.e. intermediate missing data, will not be imputed. For patients with initial disability progression based on EDSS or $\geq 20\%$ increase in 9-HPT, data collected at the next scheduled visit or treatment discontinuation visit will be used to confirm disability progression.

Every effort is made to keep the patients in the study after they withdraw from treatment, however if patients withdraw their consent to participate in the study their data will be missing after study withdrawal.

Missing data following withdrawal from study with withdrawal from treatment due to lack of efficacy will be imputed as a disability progression event at the time of withdrawal from the study.

Missing data following withdrawal from study with withdrawal from treatment due to another reason will be:

- Imputed as a disability progression event if the patient had an initial disability progression at the date of his or her last EDSS or 9-HPT assessment, whichever is the earliest
- Censored in all other cases at the date of the last EDSS or 9-HPT assessment, whichever is the earliest

Patients without any disability progression events (including imputed events) during the double-blind treatment period will be censored at the date of the last EDSS or 9-HPT assessment during the double-blind treatment period, whichever is the earliest.

4.2.3 Sensitivity Analyses for Co-Primary Estimand 1

A sensitivity analysis that adjusts for sex and duration since the onset of MS symptoms will be performed to assess the impact of these prognostic factors.

Additionally, the following sensitivity analyses will be conducted.

1. The primary analysis is performed under the assumption that patients who withdraw from study treatment due to a reason other than lack of efficacy and had an initial progression at the date of their last EDSS or 9-HPT assessment prior to initiation of another MS DMT or commercial ocrelizumab, or withdrawal from study, would have had that progression confirmed had they not initiated another MS DMT or

commercial ocrelizumab or withdrawn from the study. As this assumption could be implausible, the robustness of the estimated treatment effect to violations of this assumption will be investigated by repeating the primary analysis with the following imputation rules: For patients who withdraw from study treatment due to a reason other than lack of efficacy and had an initial progression at the date of their last EDSS or 9-HPT assessment prior to initiation of another MS DMT or commercial ocrelizumab, or withdrawal from study, multiple imputation will be used to either impute a progression event or to censor the time to onset of confirmed progression. The presence or absence of a progression event will be imputed from a Bernoulli distribution with success probability ranging from 0-1 in increments of 0.33. This procedure will be applied within arms followed by treatment effect estimation in 100 imputed data sets. An overall estimate of the treatment effect and associated standard error for computing 95% Wald intervals will be obtained by applying Rubin's rules on the log HR scale and then back transforming to the original scale:

$$\log(HR) = 1/100 \sum_{m=1}^{100} \log(HR_m) \text{ and } SE(\log(HR)) = \sqrt{V_w + \left(1 + \frac{1}{100}\right) V_B}$$

where HR_m is the HR estimated in the m th imputed data set, V_w is the sample mean of the estimated variance of $\log(HR_m)$, and V_B is the sample variance of $\log(HR_m)$. The scenarios that result in non-significant treatment effect estimates will be identified for a tipping point analysis.

2. The primary analysis is performed under the independent censoring assumption. However, this assumption may not be plausible. A similar tipping point analysis as the one described in 1. will be conducted for patients who experience censoring because of the following:
 - Initiation of another MS DMT or commercial ocrelizumab
 - Withdrawal from study (missing data)

Additionally, if at least 10% of the patients randomized to the ocrelizumab arm experience censoring because of the above, a sensitivity analysis may be performed, where it will be attempted to predict the onset of composite 12-week CDP event times for these patients using the observed profile of patients randomized to the placebo arm. The proposed approach appears conservative yet plausible for the study drug. It assumes no treatment effect after the censoring. In the placebo arm, this is compatible with a missing at random (MAR) assumption whereas in the active drug arm, the imputation is under a missing not at random (MNAR) assumption. The proposed sensitivity analysis is based on the multiple imputation approach in [Atkinson et al. 2019](#). Specifically, the following steps will be applied:

- a) Fit a Weibull model with hazard function $\alpha \cdot \text{time}^{\alpha-1} \exp\{\beta_0 + \beta_1 X_i\}$ to time to onset of composite 12-week CDP in patients randomized to the placebo arm. Here, α , β_0 , β_1 are unconstrained parameters to be estimated, time is time from randomization, X_i is a vector containing the baseline EDSS and 9-HPT values for patient i .

- b) Simulate 100 sets of $\{\alpha, \beta_0, \beta_1\}$, from the estimated asymptotic normal distribution of the maximum likelihood estimator of these parameters.
- c) Let W_i be the time from randomization for patient i at the time of withdrawal from the study or initiation of another MS DMT or commercial ocrelizumab. Let F_i be the time from randomization for patient i at the clinical cut-off date or at week 144, whichever is earlier. For each set of simulated parameter values, generate onset of composite 12-week CDP event times for patients who have not had composite 12-week CDP up to and including W_i , and where $W_i < F_i$. This will result in 100 complete analysis data sets, i.e., where composite 12-week CDP events times are either available or are censored at F_i . In order to simulate composite 12-week CDP events time O_i for patient i , the following formula will be used:

$$O_i = \{W_i^\alpha - \log(U_i) \exp(-\beta_0 - \beta_1 X_i)^\alpha\}^{\frac{1}{\alpha}}$$

Here, U_i is generated from a standard uniform distribution. If $O_i > F_i$, the onset time of composite 12-week CDP is recorded as censored at F_i in the analysis data set, otherwise it is set to O_i .

- d) For each of the 100 complete analysis data sets, estimate the log HR and its associated standard error with the Cox model used for the primary analysis. Then, use Rubin's rules to combine the estimates from the 100 complete data sets, as described in sensitivity analysis 1, to obtain an overall estimate of the treatment effect on the HR scale and associated 95% Wald interval.

4.2.4 **Supplementary Analyses for Co-Primary Estimand 1**

1. The primary analysis will be repeated after excluding patients who meet the exclusion criteria/do not meet the inclusion criteria listed below at baseline.

Inclusion criteria:

- Diagnosis of PPMS in accordance with the McDonald criteria ([Thompson et al. 2017](#))
- Age 18–65 years at time of signing Informed Consent Form
- EDSS score at screening and baseline ≥ 3.0 to 8.0, inclusive
- Disease duration from the onset of MS symptoms relative to randomization date:
 - Less than 20 years in patients with an EDSS score at screening 7.0–8.0
 - Less than 15 years in patients with an EDSS score at screening 5.5–6.5
 - Less than 10 years in patients with an EDSS score at screening ≤ 5.0
- Documented history or presence at screening of at least one of the following laboratory findings in a CSF specimen (source documentation of laboratory results and method must be verified)
 - Elevated IgG index

- One or more IgG oligoclonal bands detected by isoelectric focusing
- Screening and baseline 9-HPT completed in > 25 seconds (average of the two hands)
- Ability to complete the 9-HPT within 240 seconds with each hand at screening and baseline
- Neurological stability for ≥ 30 days prior to baseline

Exclusion criteria:

- History of relapsing-remitting or secondary progressive MS at screening
- Patients requiring symptomatic treatment of MS (e.g., fampridine) and/or physiotherapy who are not on a stable regimen. Patients must not initiate symptomatic treatment of MS or physiotherapy within 4 weeks of randomization
- Known presence of other neurologic disorders that could interfere with the diagnosis of MS or assessments of efficacy and/or safety during the study
- Any concomitant disease that may require chronic treatment with systemic corticosteroids or immunosuppressants during the course of the study
- Pregnant or breastfeeding
- Treatment with any investigational agent within 24 weeks prior to screening (Visit 1) or 5 half-lives of the investigational drug (whichever is longer), or treatment with any experimental procedure for MS (e.g., treatment for chronic cerebrospinal venous insufficiency)
- Previous treatment with B cell-targeting therapies (e.g., rituximab, ocrelizumab, atacicept, belimumab, ofatumumab, and alemtuzumab)
- Any previous treatment with bone marrow transplantation and hematopoietic stem cell transplantation
- Any previous history of transplantation or anti-rejection therapy
- Treatment with IV Ig or plasmapheresis within 12 weeks prior to randomization
- Systemic corticosteroid therapy within 4 weeks prior to screening

In addition, the hypothetical strategy will be used to handle the following intercurrent events:

- Received no study drug
- Received study drug that had been mishandled (e.g., incorrect storage temperature) and was not approved for subsequent use
- Received study drug but was not randomized
- Received prohibited disease-modifying therapy for MS
- Misadministration of study drug (e.g. overdose, incorrect study medication, patient received study drug other than the one the patient was randomized to)

- Missed two or more consecutive as per protocol 9HPT/EDSS assessments in either double-blind treatment (DBT) or FU1
- Unintended unblinding

Under this strategy, data after these intercurrent events will be treated as missing and the time to onset of composite 12-week CDP will be censored at the last assessments prior to the intercurrent event times. However, observed data after the intercurrent events will still contribute to the confirmation period for determining if an initial progression can be confirmed. This analysis estimates the treatment effect of ocrelizumab in a population who always receives the study treatment as planned and with no major protocol deviations.

2. Supplementary estimand applying treatment-policy strategy to withdrawal from study treatment and to initiation of other treatments:

This supplementary estimand will use a treatment-policy strategy to estimate the treatment effect of ocrelizumab versus placebo on disability progression, on the basis of initial treatment, regardless whether patients adhered to randomized treatment or initiated other treatments (e.g., discontinued treatment or switched to another MS DMT or commercial ocrelizumab).

3. Supplementary estimands to estimate the treatment effect had the patient not withdrawn from study treatment:

The supplementary estimands will use a hypothetical strategy to estimate the treatment effect of ocrelizumab versus placebo on disability progression had the patient not withdrawn from study treatment as follows:

- The same estimand as the primary analysis for the Oratorio study (WA25046): If the patient withdraws from treatment without any prior events, an event is imputed as if the patient had an initial disability progression at the date of his or her last EDSS or 9-HPT assessment prior to withdrawal from treatment, whichever is the earliest, and no follow-up data are available, otherwise the patient is censored in all other cases at the date of the last EDSS or 9-HPT assessment prior to withdrawal from treatment, whichever is the earliest.
- Estimand counting withdrawal due to lack of efficacy as treatment failure: This estimand will estimate the treatment effect measured as time to disease progression or discontinuation from the randomized treatment due to lack of efficacy (composite endpoint). Same as the estimand above (Study WA25046); however, patients who withdrew from treatment due to lack of efficacy will also have an imputed event.
- Estimand counting withdrawal due to lack of efficacy or due to adverse events as treatment failure: This estimand will estimate the treatment effect measured as time to disease progression or discontinuation from the randomized treatment due to lack of efficacy or due to an adverse event (composite

endpoint). Same as the estimand above (Study WA25046); however, patients who withdrew from treatment due to lack of efficacy or due to an adverse event will also have an imputed event.

4.2.5 Main Analytical Approach for Co-Primary Estimand 2

The co-primary estimand 2 will be similar to the co-primary estimand 1 except the population will be patients with PPMS, including patients later in their disease course, as defined by the study inclusion and exclusion criteria (see Sections 4.1.1 and 4.1.2 of the protocol).

4.2.6 Sensitivity Analyses for Co-Primary Estimand 2

The sensitivity analysis for co-primary estimand 2 will be similar to the sensitivity analysis for co-primary estimand 1 except the population will be patients with PPMS, including patients later in their disease course, as defined by the study inclusion and exclusion criteria (see Sections 4.1.1 and 4.1.2 of the protocol).

4.2.7 Supplementary Analyses for Co-Primary Estimand 2

The supplementary analyses for co-primary estimand 2 will be similar to the supplementary analyses for co-primary estimand 1 except the population will be patients with PPMS, including patients later in their disease course, as defined by the study inclusion and exclusion criteria (see Sections 4.1.1 and 4.1.2 of the protocol).

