MRI activity analysis set	All randomized participants with MRI activity, defined as presence of T1 Gd+ lesion[s] and/or new and/or enlarging T2 lesion[s] as detected by MRI scans during the screening phase; participants will be included in the analysis according to the treatment to which they were assigned.
Immunogenicity analysis set	All randomized participants with at least one ADA assessment; participants will be grouped according to treatment received at first exposure or, if no treatment is received prior to study discontinuation, according to treatment assigned.

Participant Analysis Set	Description
Pharmacokinetic analysis set	All randomized participants who have measurable concentrations of ocrelizumab unless major protocol deviations or unavailability of information (e.g., exact blood sampling time) occurred or if data are unavailable, not plausible, or incomplete which may interfere with PK evaluation. Excluded cases will be documented together with the reason for exclusion; participants will be grouped together.
Safety analysis set	All participants who received at least one infusion (partial or complete) of study drug; participants will be included in the analyses according to the treatment that they actually received.
Ocrelizumab exposed analysis set	All randomized participants who received at least one infusion (partial or complete) of ocrelizumab (study drug, PDP OCR, OLE OCR or commercial ocrelizumab); participants will be grouped together.
No major protocol deviation (MRI activity) analysis set	All participants included in the first supplementary analysis as described in Section 4.2.4; participants will be included in the analysis according to the treatment to which they were assigned.
No major protocol deviation analysis set	All participants included in the first supplementary analysis of Section 4.2.7 participants will be included in the analysis according to the treatment to which they were assigned.

ADA = anti-drug antibody; MRI = magnetic resonance imaging; OCR = ocrelizumab; OLE = open-label extension; PDP = post-double-progression; PK = pharmacokinetic.

MRI activity analysis set will be used in the analysis of the co-primary estimand 1.

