4. STATISTICAL ANALYSES

4.1 GENERAL CONSIDERATIONS

As per the EMA guideline on multiplicity issues in clinical trials (EMA, 2017) and the FDA guidance for industry on multiple endpoints in clinical trials (FDA, 2022) multiple primary endpoints are designated as co-primary endpoints if study success is defined by a positive outcome in all primary endpoints.

In this SAP, the terminology co-primary endpoint and co-primary estimand is used although study success is defined by a positive outcome in at least one of the two co-primary endpoints, analogous to multiple primary endpoints.

For all continuous variables for which descriptive statistics are reported, the following will be reported: the number of observations, the mean, median, standard deviation, and minimum and maximum. The 25th and 75th percentiles (Q1 and Q3) will also be reported for selected tables. Descriptive summaries of discrete data will include frequencies expressed in terms of number and percentage of patients.

All primary and secondary efficacy endpoints will be stratified by/adjusted for:

- MRI activity, defined as any T1 Gd+ lesion(s) and/or new and/or enlarging T2 lesion(s) during the screening period (yes vs. no)
- Age (≤ 55 . vs. > 55)
- EDSS score (≤ 6.5 vs. > 6.5)
- Region (two regions: European Union, United Kingdom, and Canada vs. other)

The baseline is defined as the most recent value prior to first dose administration (or up to and including the date of randomization for non-treated patients), unless specified otherwise.

The baseline MRI is defined as the most recent MRI prior to randomization.

For EDSS and 9-HPT, baseline is defined as the most recent value prior to randomization.

There will be no imputation of the baseline outcome value, with the consequence that participants missing the baseline outcome measure will not contribute to the analyses which use change from baseline of a given outcome measure as the dependent variable.

For analysis purposes, the time of treatment discontinuation will be defined as 24 weeks after the last dose prior to the date of treatment discontinuation recorded in the electronic Case Report Form (eCRF).

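### SAP 4.2.3 item 2(c) starts the placebo-based imputation at withdrawal or therapy switch, not at the primary censoring date, so unobserved time counts as event-free in both arms

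*SAP*

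**What the plan says.** SAP 4.2.2 deals with patients who start another therapy, did not stop treatment for lack of efficacy and had no unconfirmed progression pending. The rule is "Censored in all other cases at the date of the last EDSS or 9-HPT assessment prior to the initiation of another treatment", using the earlier of the two assessment dates. Study withdrawal is handled in the same way.

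SAP 4.2.3, item 2, then tests the independent-censoring assumption for these patients. A Weibull model is fitted to the placebo arm, and step (c) sets the starting point: "Let W_i be the time from randomization for patient i at the time of withdrawal from the study or initiation of another MS DMT"; a switch to commercial ocrelizumab is treated alike. The analyst is to "generate onset of composite 12-week CDP event times for patients who have not had composite 12-week CDP up to and including W_i". Time is measured from randomization throughout.

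On what the method represents, the SAP says "It assumes no treatment effect after the censoring", calls the placebo-arm imputation compatible with missing at random, and adds "The proposed approach appears conservative yet plausible for the study drug". It gives no figure for the expected shift. The analysis is optional and is considered only if at least 10% of the ocrelizumab arm is censored for these reasons. SAP 4.2.6 carries it over to the all-randomized population.

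**The concern.** Progression status is known only up to the last assessment. Step (c) nevertheless conditions on no event up to W_i, which can be later. Between the two dates no imputed patient can have an event, so the placebo profile does not begin at censoring as the SAP says it does. On placebo, guaranteed event-free time that nobody observed is not a missing-at-random assumption.

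At stake is whether the analysis matches its description, and whether the resulting hazard ratio depends on how long after the last visit a withdrawal or switch is dated. That dependence grows when the arms lose patients at different rates, which is when this analysis is most likely to be consulted.

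**Working it through.** **1. The two starting points.** Let L be the primary censoring date, W the date in step (c), F the end of follow-up and H the placebo cumulative hazard.

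- As written: P(imputed event) = 1 − exp{−[H(F) − H(W)]}.
- From the last assessment: P = 1 − exp{−[H(F) − H(L)]}.
- Difference: exp{−[H(F) − H(W)]} × (1 − exp{−[H(W) − H(L)]}).

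The second factor is the event risk in the gap. It is zero only if W = L.

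**2. The plan's own figure (SAP 2.2).** For 340 events, HR 0.70 and two-sided alpha 0.0146, power = Φ(√340/2 × |ln 0.70| − 2.442) = Φ(3.288 − 2.442) = 0.801. The stated figure is about 80%, so the design inputs are reproduced.

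**3. Risk hidden in the gap.** A placebo rate of 40% at Week 120 gives a hazard of −ln(0.60)/120 = 0.00426 per week.

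- 6-week gap: 1 − exp(−0.00426 × 6) = 2.5% per censored patient.
- 12-week gap: 1 − exp(−0.00426 × 12) = 5.0%.
- MRI-active set (44%): −ln(0.56)/120 = 0.00483 per week, so 5.6% over 12 weeks.

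EDSS and 9-HPT are scheduled every 12 weeks in double-blind treatment and FU1 (Protocol 4.5.7 and Appendices 1 and 2), so 12 weeks is the usual upper size of the gap.

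**4. Patients affected.** Dropout of 10% a year is −ln(0.90)/52 = 0.00203 per week. The ocrelizumab event hazard at HR 0.70 is 0.70 × 0.00426 = 0.00298. The share dropping out before an event within 144 weeks is 0.00203/0.00501 × (1 − exp(−0.00501 × 144)) = 0.405 × 0.514 = 21%. The 10% trigger would be met.

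**5. Effect on the hazard ratio.** This was simulated with exponential times (Weibull shape 1), true HR 0.70 and placebo-hazard imputation in both arms, followed by Cox regression. There were 4 million patients per row, with a Monte Carlo SE of 0.0016. The gap lengths and the unequal dropout rates are assumptions. In the mean-6-week rows, L is the last 12-weekly visit before dropout.

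| Annual dropout, placebo / ocrelizumab | Gap | Start at L | Start at W | W minus L |
|---|---|---|---|---|
| 10% / 10% | mean 6 weeks | 0.740 | 0.738 | −0.002 |
| 10% / 10% | 12 weeks | 0.739 | 0.736 | −0.003 |
| 10% / 20% | mean 6 weeks | 0.774 | 0.765 | −0.009 |
| 10% / 20% | 12 weeks | 0.779 | 0.757 | −0.022 |
| 20% / 10% | mean 6 weeks | 0.737 | 0.742 | +0.005 |
| 20% / 10% | 12 weeks | 0.740 | 0.750 | +0.010 |

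A separate set of 400 trials of 1000 patients, with 25 imputations and Rubin's rules, gave 0.740 against 0.736 for equal dropout and a 12-week gap. With equal dropout, the later start removes about 2 events per arm at a mean 6-week gap and about 3.6 per arm at 12 weeks. The losses are similar in the two arms, so they largely cancel.

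**6. Effect on the conclusion.** In the trial-level simulations, rejection at 0.0146 was the same under both starts with equal dropout (69.8% at a mean 6-week gap, 68.0% at 12 weeks). With ocrelizumab dropout at 20% and a 12-week gap it was 42% from L and 52% from W.

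**7. Covariates.** In step (a), "X_i is a vector containing the baseline EDSS and 9-HPT values for patient i", whereas the final Cox model is stratified by MRI activity, age, EDSS and region. The plan's rates imply an inactive placebo rate of (0.40 × 1000 − 0.44 × 350)/650 = 37.8%. Adding MRI activity to the imputation model changed the all-randomized HR by 0 to ±0.002, with the sign depending on which stratum drops out more.

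**The case against.** **The gap may be close to zero.** Treatment-discontinuation and withdrawal-from-follow-up visits are planned, with EDSS and 9-HPT scheduled at them (Protocol 4.7.1, 4.7.2, Appendices 1 and 2). This stands for patients who attend. It does not cover loss to follow-up, and no assessment is tied to the start of another therapy during FU1. Using the earlier of two assessment dates can only lengthen the gap.

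**Starting at the last assessment is itself a choice.** One could apply each arm's own hazard from L to W and the placebo hazard after that. At the plan's dropout rate this gave event-rate-ratio HRs of 0.735, 0.730 and 0.725 when W falls 0, 12 or 24 weeks after dropout, against 0.736, 0.732 and 0.727 as written. So with balanced dropout the written rule is no softer than that defensible alternative. But the SAP does not describe that alternative. It describes no treatment effect after the censoring, and the censoring is at L.

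**Little rests on this analysis.** It is conditional and optional, and the same item commits to a tipping-point analysis of the same patients. Both are true, and they keep the point minor.

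**Stronger readings that the documents do not support.** A reader might infer that the test is generally softer than claimed; the sign reverses when placebo dropout is higher, and the SAP states no strength to fall short of. A reader might infer that the clock restarts at W_i; the formula keeps time from randomization and conditions on survival to W_i. A reader might infer that leaving out the strata biases the result. EDSS is already in the model, and for the population of 4.2.3, "MRI activity analysis set will be used in the analysis of the co-primary estimand 1", so MRI activity is constant if the model is fitted in that set.

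**Conclusion.** The inconsistency is real. The primary analysis censors at the last EDSS or 9-HPT assessment, while step (c) treats the time from there to W_i as event-free in imputed patients of both arms, against the SAP's own description of the method.

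Its size is small under the plan's equal 10% dropout: an HR lower by about 0.002 to 0.004 for gaps of up to 12 weeks, with rejection unchanged. It becomes noticeable only with unequal dropout: about 0.01 to 0.02 lower at 20% on ocrelizumab against 10% on placebo, and up to about 0.01 higher in the reverse case. No direction should be asserted in advance.

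These figures rest on exponential times, the all-randomized design rates, and assumed gaps and dropout imbalances. At Weibull shape 1 the printed simulation formula agrees with the stated hazard, so the result does not depend on how that formula is parametrised.

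**What to change.** In SAP 4.2.3 item 2(c), define W_i as the primary-analysis censoring time: the earlier of the last EDSS and last 9-HPT dates before study withdrawal or before the new therapy, as in 4.2.2. The change then applies to the all-randomized analysis through 4.2.6. Reporting the interval from last assessment to withdrawal or switch by arm would show how much the choice matters.

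Optionally, add the randomization factors to X_i for the all-randomized analysis, to match the stratified Cox model; the expected effect is negligible.

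The cost is one changed definition before database lock. No new data are needed.
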